Clinical Trial Protocol: ADX-102-DED-032

Protocol Title: A Randomized, Double-Masked, Parallel-Group, Vehicle-Controlled Phase 3 Clinical Trial to Assess the Efficacy and Safety of 0.25% Reproxalap Ophthalmic Solution Compared to Vehicle in Subjects with Dry Eye Disease

Protocol Number: ADX-102-DED-032

Study Phase: 3

[figure not shown]
Test Article Name: 0.25% Reproxalap Ophthalmic Solution

IND Number: 134734

Indication: Dry Eye Disease

Sponsor: Aldeyra Therapeutics, Inc.
[name]
[name]

IRB/IEC:

Date

Original Protocol: 19Apr2024

Confidentiality Statement

This protocol contains confidential, proprietary information [REDACTED] and Aldeyra Therapeutics, Inc. Further dissemination, distribution, or copying of this protocol or its contents is strictly prohibited.

STUDY PERSONNEL

SPONSOR PERSONNEL

Chief Development Officer:	
	
Department Senior Vice President:	
Department Senior Director:	
Clinical Project Manager:	

MEDICAL MONITOR

Medical Monitor:	
-------------------------	--

SYNOPSIS

Protocol Title:	A Randomized, Double-Masked, Parallel-Group, Vehicle-Controlled Phase 3 Clinical Trial to Assess the Efficacy and Safety of 0.25% Reproxalap Ophthalmic Solution Compared to Vehicle in Subjects with Dry Eye Disease
Protocol Number:	ADX-102-DED-032
Test Article:	0.25% Reproxalap Ophthalmic Solution (reproxalap)
Study Phase:	3
Primary Objective(s):	To evaluate the efficacy of reproxalap, as assessed by an ocular symptom during exposure to the [REDACTED] (CAE) in subjects with dry eye disease
Overall Study Design:	
Structure:	Double-masked, randomized, parallel-group trial
Duration:	Approximately 16-32 days per subject
Controls:	Vehicle Ophthalmic Solution (vehicle)
Dosage:	
Vehicle will be administered once approximately 5 minutes prior to the CAE entry and once approximately 50 minutes after initiation of the CAE at Visit 1.
 
Test article will be dosed topically in both eyes. Test article will be administered four times (QID) at Visit 2. At Visit 3, test article will be administered once approximately 5 minutes prior to CAE entry and once approximately 50 minutes after initiation of the CAE.

Summary of Visit Schedule:	
Three visits over the course of approximately 2 weeks:
 
 • Visit 1 = Day -14 -16/+2, screening, vehicle CAE • Visit 2 = Day 1, randomization, QID test article administration • Visit 3 = Day 2, test article CAE, trial exit 
At Visit 2, subjects will be randomized 1:1 to receive either reproxalap or vehicle for Visit 2 and Visit 3.

Measures Taken to Reduce Bias:	ADX-102-DED-032 is a randomized treatment assignment, double-masked trial.
Study Population Characteristics:	

Number of Subjects:	Approximately 110 subjects are expected to be enrolled in the trial.
Inclusion Criteria:	
Subjects must meet all of the following criteria:
 
1. 18 years of age (either gender and any race);2. Ability to provide written informed consent and sign the Health Information Portability and Accountability Act (HIPAA) form;3. Reported history of ocular discomfort associated with dry eye disease for at least 6 months prior to Visit 1;4. Reported history of use or desire to use eye drops for dry eye symptoms within 6 months of Visit 1; 
[REDACTED]
 
[REDACTED]
 
[REDACTED]
 
[REDACTED]

Exclusion Criteria:	
Subjects must not meet any of the following criteria:
 
[REDACTED]
 
[REDACTED]
 
2. Clinically significant slit lamp findings at Visit 1 that may include active blepharitis, meibomian gland dysfunction, lid margin inflammation, or active ocular allergies that require therapeutic treatment, and/or in the opinion of the investigator may interfere with study parameters;3. Diagnosis of an ongoing ocular infection (bacterial, viral, or fungal), or active ocular inflammation at Visit 1;4. Contact lens use within 7 days of Visit 1 or anticipated use of contact lenses during the trial;5. Artificial tear eye drop use within 2 hours of Visit 1 or within 24 hours of Visit 2 (drops cannot be used on the day of Visit 2 or Visit 3);6. Previous laser-assisted in situ keratomileusis surgery within the last 12 months;

	
7. Use of topical ocular cyclosporine, lifitegrast, or corticosteroid within 90 days of Visit 1;8. Systemic corticosteroid or other immunomodulator therapy (not including inhaled corticosteroids) within 14 days of Visit 1, or any planned immunomodulatory therapy throughout the clinical trial;9. Planned ocular and/or lid surgeries throughout the clinical trial or any ocular surgery within 6 months of Visit 1;10. Temporary punctal plugs during the trial that have not been stable within 30 days of Visit 1;11. Use of and unwillingness to discontinue topical ophthalmic prescriptions (including medications for glaucoma) or over-the-counter solutions (not including artificial tears), gels, or scrubs for the duration of the trial (excluding medications allowed for the conduct of the trial);12. Corrected visual acuity greater than or equal to logarithm of the minimum angle of resolution (logMAR) + 0.7 as assessed by Early Treatment of Diabetic Retinopathy Study (ETDRS) scale in both eyes at Visit 1;13. Pregnancy, nursing, or planned pregnancy during the conduct of the trial;14. Unwillingness to submit a urine pregnancy test at Visit 1 and Visit 3 (or early termination visit) if of childbearing potential (non-childbearing potential is defined as a woman who is permanently sterilized [e.g., has had a hysterectomy or tubal ligation], or is post-menopausal [without menses for 12 consecutive months].);15. If of childbearing potential (female or male), unwillingness to use an acceptable means of birth control (Acceptable methods of contraception include: hormonal – oral, implantable, injectable, or transdermal contraceptives; mechanical – spermicide in conjunction with a barrier such as a diaphragm or condom; intrauterine device [IUD]; or surgical sterilization of partner. For non-sexually active males or females, abstinence may be regarded as an adequate method of birth control; however, if the subject becomes sexually active during the trial, he/she must agree to use adequate birth control as defined above for the remainder of the trial.);
--	--

	
16. Known allergy and/or sensitivity to the test article or test article components;17. A condition that the investigator feels may put the subject at significant risk, may confound the trial results, or may interfere significantly with participation in the trial;18. Current enrollment in an investigational drug or device trial or previous use of an investigational drug or device within 30 days of Visit 1; 19. [REDACTED] 20. Current use of any medication known to cause ocular drying that is not used on a stable dosing regimen for at least 30 days prior to Visit 1; or21. Inability or unwillingness to follow instructions, including participation in all assessments and visits.
--	---

Evaluation Criteria:

Primary Endpoint:	Ocular discomfort symptom score (0 – 100 VAS) over 100 minutes in the CAE at Visit 1 and Visit 3
Safety Endpoints:	
• Visual acuity• Slit lamp examination• Adverse event query• Intraocular pressure

General Statistical Methods and Types of Analyses:

Statistical analyses will be detailed in the statistical analysis plan, which will dominate any statistical language herein. Any changes to protocol-stated analyses will also be detailed in the statistical analysis plan.

Sample Size:

[REDACTED]

[REDACTED]

[REDACTED]

[REDACTED]

Primary Efficacy Analysis:

The primary endpoint will be assessed using the intent-to treat (ITT) population with observed data only. The ITT population includes all randomized subjects.

Safety Analyses:

Safety endpoints will be summarized using descriptive statistics. For qualitative safety assessments, counts and percentages will be reported at the eye level and subject level, where appropriate. For quantitative safety assessments, endpoints will be summarized at the eye level using continuous summary statistics.

Summary of Known and Potential Risks and Benefits to Human Subjects:

Potential risks and benefits are described in the Investigator's Brochure.

TABLE OF CONTENTS

Clinical Trial Protocol: ADX-102-DED-032	1
SYNOPSIS	3
TABLE OF CONTENTS	8
List of Abbreviations	11
1 INTRODUCTION	12
2 STUDY OBJECTIVE	13
3 CLINICAL HYPOTHESES	13
4 OVERALL STUDY DESIGN	13
5 STUDY POPULATION	13
5.1 Number of Subjects (approximate)	13
5.2 Study Population Characteristics	13
5.3 Inclusion Criteria	13
5.4 Exclusion Criteria	14
5.5 Withdrawal Criteria (if applicable)	15
6 STUDY PARAMETERS	15
6.1 Primary Endpoint	15
6.2 Safety Endpoints	15
7 STUDY MATERIALS	16

Appendix 1: Schedule of Visits and Measurements.....	31
Appendix 2: Prohibited Medications List.....	32
Appendix 3: Examination Procedures, Tests, Equipment, and Techniques	35
Appendix 4: Amendment Summary of Changes Table.....	39
Appendix 5: Sponsor and [REDACTED] Approvals	40
Appendix 6: Investigator's Signature	41

List of Abbreviations

CFR	Code of Federal Regulations
ETDRS	Early Treatment of Diabetic Retinopathy Study
HIPAA	Health Information Portability and Accountability Act
ICF	informed consent form
IEC	Independent Ethics Committee
IRB	institutional/independent review board
ITT	intent-to-treat
LogMAR	logarithm of the minimum angle of resolution
MMRM	mixed model repeated measures
OTC	over the counter
PP	per protocol
QID	four times daily
RASP	reactive aldehyde species
TEAE	treatment-emergent adverse event
VAS	visual analog scale

1 INTRODUCTION

2 STUDY OBJECTIVE

To evaluate the efficacy of reproxalap, as assessed by an ocular symptom (ocular discomfort) during exposure to the CAE in subjects with dry eye disease.

3 CLINICAL HYPOTHESES

The clinical hypothesis is that reproxalap is more effective than vehicle in reducing subject-reported ocular discomfort.

4 OVERALL STUDY DESIGN

ADX-102-DED-032 is a Phase 3, randomized, double-masked, parallel-group, vehicle-controlled trial designed to evaluate the efficacy and safety of reproxalap compared to vehicle in subjects with dry eye disease. Approximately 110 subjects will be enrolled in the trial. Male and female subjects at least 18 years of age with a subject-reported history of dry eye disease and meeting all other eligibility criteria will be randomized to receive reproxalap or vehicle in a 1:1 ratio (approximately 55 subjects in each treatment arm).

5 STUDY POPULATION

5.1 Number of Subjects (approximate)

Approximately 180 subjects will be screened to enroll approximately 110 subjects across approximately 2 sites.

5.2 Study Population Characteristics

All subjects must be at least 18 years of age, be of either sex and of any race, have a subject-reported history of dry eye disease, and meet all of the inclusion criteria and none of the exclusion criteria.

5.3 Inclusion Criteria

Each subject must meet each of the following criteria:

1. 18 years of age (either gender and any race);
2. Ability to provide written informed consent and sign the Health Information Portability and Accountability Act (HIPAA) form;
3. Reported history of ocular discomfort associated with dry eye disease for at least 6 months prior to Visit 1;
4. Reported history of use or desire to use eye drops for dry eye symptoms within 6 months of Visit 1;

5.4 Exclusion Criteria

Each subject may not meet any of the following criteria:

- 2. Clinically significant slit lamp findings at Visit 1 that may include active blepharitis, meibomian gland dysfunction, lid margin inflammation, or active ocular allergies that require therapeutic treatment, and/or in the opinion of the investigator may interfere with trial parameters;
- 3. Diagnosis of an ongoing ocular infection (bacterial, viral, or fungal), or active ocular inflammation at Visit 1;
- 4. Contact lens use within 7 days of Visit 1 or anticipated use of contact lenses during the trial;
- 5. Artificial tear eye drop use within 2 hours of Visit 1 or within 24 hours of Visit 2 (drops cannot be used on the day of Visit 2 or Visit 3);
- 6. Previous laser-assisted *in situ* keratomileusis (LASIK) surgery within the last 12 months;
- 7. Use of topical ocular cyclosporine, lifitegrast, or corticosteroid within 90 days of Visit 1;
- 8. Systemic corticosteroid therapy or other immunomodulator (not including inhaled corticosteroids) within 14 days of Visit 1 or anticipate such therapy throughout the clinical trial;
- 9. Planned ocular and/or lid surgeries throughout the clinical trial or any ocular surgery within 6 months of Visit 1;
- 10. Temporary punctal plugs during the trial that have not been stable within 30 days of Visit 1;
- 11. Use of and unwillingness to discontinue topical ophthalmic prescriptions (including medications for glaucoma) or over-the-counter solutions (not including artificial tears), gels or scrubs for the duration of the trial (excluding medications allowed for the conduct of the trial);
- 12. Corrected visual acuity greater than or equal to logarithm of the minimum angle of resolution (logMAR) + 0.7 as assessed by Early Treatment of Diabetic Retinopathy Study (ETDRS) scale in both eyes at Visit 1;
- 13. Pregnancy, nursing, or planned pregnancy during the conduct of the trial;
- 14. Unwillingness to submit a urine pregnancy test at Visit 1 and Visit 3 (or early termination visit) if of childbearing potential. (non-childbearing potential is defined as a woman who is permanently sterilized [e.g., has had a hysterectomy or tubal ligation], or is post-menopausal [without menses for 12 consecutive months]);

15. If of childbearing potential (female or male), unwillingness to use an acceptable means of birth control. (Acceptable methods of contraception include: hormonal – oral, implantable, injectable, or transdermal contraceptives; mechanical – spermicide in conjunction with a barrier such as a diaphragm or condom; intrauterine device [IUD]; or surgical sterilization of partner. For non-sexually active males or females, abstinence may be regarded as an adequate method of birth control; however, if the subject becomes sexually active during the trial, he/she must agree to use adequate birth control as defined above for the remainder of the trial);
16. Known allergy and/or sensitivity to the test article or test article components;
17. A condition that the investigator feels may put the subject at significant risk, may confound the trial results, or may interfere significantly with participation in the trial;
18. Current enrollment in an investigational drug or device trial or previous use of an investigational drug or device within 30 days of Visit 1;
[REDACTED]
20. Current use of any medication known to cause ocular drying that is not used on a stable dosing regimen for at least 30 days prior to Visit 1; or
21. Inability or unwillingness to follow instructions, including participation in all assessments and visits.

5.5 Withdrawal Criteria (if applicable)

Subjects may voluntarily withdraw from the trial at any time. Additionally, subjects may be discontinued for safety reasons as determined by the investigator and/or Medical Monitor.

6 STUDY PARAMETERS

6.1 Primary Endpoint

Ocular discomfort symptom score (0 – 100 VAS) over 100 minutes in the CAE at Visit 1 and Visit 3

6.2 Safety Endpoints

- Visual acuity
- Slit lamp examination
- Adverse event query
- Intraocular pressure

7 STUDY MATERIALS

7.1 Study Treatment(s)

7.1.1 Test Article and Vehicle Packaging Configuration

[REDACTED]

7.1.2 Test Article Storage and Accountability

[REDACTED]

The test article is to be used only in accordance with this protocol. The test article must be distributed only to subjects properly qualified under this protocol to receive test article. The investigator must keep an accurate accounting of the test article by maintaining a detailed inventory, including the amount of test article received by the site, amount used, and the amount returned to the Sponsor upon the completion of the trial.

7.1.3 Instructions for Dispensation, Use, and Administration

- At Visit 1, qualified subjects will be assigned a vehicle kit. Subjects will use two vials from the kit for Visit 1 in-office doses. After use, vials will be placed into a zip locked bag labeled with the subject's initials and screening number for accountability.
- At Visit 2, qualified subjects will be randomized and will be assigned a single kit of reproxalap or vehicle. Subjects will be dosed at the clinical site four times. (3 hours between Dose 1 and Dose 2, 30 minutes between Dose 2 and Dose 3, 30 minutes between Dose 3 and Dose 4) by trained site staff.
- At Visit 3, subjects will be dosed two times at the clinical site (approximately 5 minutes prior to CAE entry and approximately 50 minutes after CAE entry) from the same kit by trained site staff.
- Subjects will be instructed to close their eyes for two minutes after instillation.

7.2 Other Study Supplies

[REDACTED]

8 STUDY METHODS AND PROCEDURES

8.1 Subject Entry Procedures

8.1.1 Overview

Subjects as defined by the criteria in section 5.2, 5.3, and 5.4 will be considered for entry into the trial.

8.1.2 Informed Consent

Prior to participation in the clinical trial, the clinical trial will be discussed with the subjects, and subjects wishing to participate must give written informed consent using an informed consent form. The informed consent form must be the most recent version that has received approval/favorable review by a properly constituted Independent Review Board.

8.1.3 Washout Intervals

Prohibited medications, treatments, and activities are outlined in the exclusion criteria.

8.1.4 Procedures for Final Study Entry

Subjects must satisfy all of the inclusion criteria and none of the exclusion criteria in order to be entered into the trial.

8.1.5 Methods for Assignment to Treatment Groups:

At Visit 1 each subject who signs the informed consent will be assigned a screening number. All screening numbers will be assigned in strict numerical sequence at each site and no numbers will be skipped or omitted.

At Visit 2, a subject who meets all the eligibility criteria will be randomized to receive reproxalap or vehicle in a 1:1 ratio. Subjects will be assigned a randomization number and kit number via interactive web response system.

Both the randomization number and the assigned test article kit number will be recorded on the patient's source document and electronic Case Report Form (eCRF).

8.2 Concurrent Therapies

The use of any applicable concurrent medications (prescription or OTC) is to be recorded on the subject source document along with the reason the medication was taken.

Concurrent enrollment in an investigational drug or medical device trial is not permitted.

8.2.1 Prohibited Medications/Treatments

Prohibited medications, treatments, and activities are outlined in the exclusion criteria and Appendix 2.

8.2.2 Escape Medications

Not applicable

8.2.3 Special Diet or Activities

Not applicable

8.3 **Examination Procedures**

8.3.1 Procedures to be Performed at the Study Visit with Regard to Trial Objective(s)

Visit 1 (Day -14 -16/+2, screening, vehicle CAE)

- Informed consent and HIPAA
- Demographics (e.g., gender, date of birth, race, ethnicity)
- Medical/medication & ocular history
- Urine pregnancy test (as needed)
- Subject-reported ocular discomfort (0-100 VAS)
- Visual acuity (ETDRS)
- Slit lamp examination
- Fluorescein staining
- Inclusion/exclusion criteria review
- In-office vehicle instillation by trained site staff (approximately 5 minutes prior to CAE entry)
- CAE exposure (100 minutes, vehicle administration at approximately 50 minutes) with subject-reported ocular discomfort collected at 10, 15, 20, 25, 30, 35, 40, 45, 65, 70, 75, 80, 85, 90, 95, and 100 minutes in the CAE
- CAE exit
- Slit lamp examination
- Intraocular pressure
- Schedule for Visit 2

Visit 2 (Day 1, randomization, QID test article administration)

- Medical/medication update
- Adverse event query
- Visual acuity (ETDRS)
- Slit lamp examination
- Subject-reported ocular discomfort prior to randomization (0-100 VAS)
- Inclusion/exclusion criteria review
- Randomization/enrollment
- In-office Dose #1

- In-office Dose # 2
[REDACTED]
- In-office Dose #3
[REDACTED]
- In-office Dose #4
- Subjects will return to clinic the following day

Visit 3 (Day 2, test article CAE, trial exit)

- Medical/medication update
- Adverse event query
- Urine pregnancy test (as needed)
- Visual acuity (ETDRS)
- Slit lamp examination
- Subject-reported ocular discomfort (0-100 VAS)
- In-office test article instillation by trained site staff (approximately 5 minutes prior to CAE entry)
- CAE exposure (100 minutes, test article administration at approximately 50 minutes) with subject-reported ocular discomfort collected at 10, 15, 20, 25, 30, 35, 40, 45, 65, 70, 75, 80, 85, 90, 95, and 100 minutes in the CAE
- CAE exit
- Slit lamp examination
- Intraocular pressure
- Trial exit

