8.7 Study Duration

Participation in the clinical trial is estimated to be approximately 2 weeks per subject.

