5.1 General Trial Design

ADX-102-DED-032 is a randomized, double-masked, vehicle-controlled, parallel-group clinical trial to assess efficacy and safety of reproxalap compared to vehicle in subjects with dry eye disease. The clinical trial will consist of 3 visits to the clinic over a period of approximately two weeks. Visit 1 will consist of screening and pre-CAE baseline (specific to Visit 1) assessments with response to vehicle in the CAE. Randomization will occur at Visit 2. Prior to randomization at Visit 2, a pre-dose baseline (specific to Visit 2 and Visit 3) assessment will be collected. After randomization at Visit 2, subjects will be administered four doses of randomized treatment outside the CAE. Visit 3 will consist of response to randomized treatment in the CAE. Statistical analyses are tailored to evaluate the impact of reproxalap under conditions that *facilitate* dry eye symptoms through the presence of the CAE (Visit 1 and Visit 3), and are designed to accommodate various sources of pre-specified variation such as time of collection, to provide error variation, and to provide within-subject statistical testing across repeated measures.

Trial visits will be referred to in all tables and listings as the scheduled Visit. The following table shows the scheduled trial visits, the planned trial day (note that there is no Day 0, and that Day 1 corresponds to the day of randomization), and the acceptable visit window for each trial visit.

Scheduled Visit	Planned Trial Day	Visit Window	Visit Description
Visit 1	Day -14	-14 TO -16	Screening/CAE vehicle treatment visit
Visit 2	Day 1	N/A	Randomization/outside of CAE treatment visit
Visit 3	Day 2	N/A	CAE randomized treatment (reproxalap or vehicle) visit

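### SAP 5.1 accepts Visit 1 only from Day -16 to Day -14, while the protocol permits Day -30 to Day -12, and the SAP declares no departure

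*Protocol*

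**What the plan says.** The protocol gives the Visit 1 window twice, identically. The synopsis has "Visit 1 = Day -14 -16/+2, screening, vehicle CAE" and section 8.3.1 has "Visit 1 (Day -14 -16/+2, screening, vehicle CAE". Section 8.3.1 gives the later visits as single days without a numeric window: "Visit 2 (Day 1, randomization, QID test article administration" and "Visit 3 (Day 2, test article CAE, trial exit".

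On length of participation, the synopsis gives "Approximately 16-32 days per subject". Elsewhere the protocol is looser: "Three visits over the course of approximately 2 weeks" in the synopsis and "Participation in the clinical trial is estimated to be approximately 2 weeks per subject" in section 8.7.

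The SAP 5.1 table is introduced as showing the planned day "and the acceptable visit window for each trial visit". For Visit 1 it gives planned Day -14 and a window of -14 to -16. For Visits 2 and 3 the window is marked not applicable. The same section states that there is no Day 0 and that Day 1 is the day of randomization.

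Four other parts of the SAP bear on how that cell is used:
- SAP 1 says that the SAP prevails over the protocol where their directives differ.
- SAP 2, the section for departures from the protocol, lists none and describes the planned analyses as compatible with the protocol.
- SAP 12 summarizes major protocol deviations and names visits outside their window as one category.
- SAP 10.2 removes subjects with a major deviation from the per-protocol population, which SAP 19 uses for a sensitivity analysis of the primary endpoint.

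**The concern.** The two documents give different acceptable dates for the same visit, and the SAP's range is much the narrower. Visit 1 is the only visit with a numeric window in the readable text of either document. The SAP 5.1 cell is therefore the only numeric standard the readable SAP offers for its own out-of-window category. SAP 12 does not say which document's window is to be used, and the SAP's precedence rule points towards its own.

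If the cell is applied as written, a subject screened on a date the protocol allows could appear in the deviation summary and in the listing of deviations. If that deviation were also graded major, the subject would leave the per-protocol analysis. The accuracy of deviation reporting and the make-up of one sensitivity population are at stake; the primary result is not.

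**Working it through.** **Inputs**
- Protocol (synopsis and 8.3.1): Visit 1 target Day -14, window -16/+2; Visit 3 on Day 2.
- Protocol synopsis: duration about 16 to 32 days.
- SAP 5.1: Visit 1 window -14 to -16; no Day 0.

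**Step 1: use the protocol's duration to check how its window should be read.** With no Day 0, the inclusive span from Visit 1 on Day -d to Visit 3 on Day 2 is d + 2 days.

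| Visit 1 | Span to Day 2 | Comparison with 16 to 32 days |
|---|---|---|
| Day -30 (protocol early edge) | 30 + 2 = 32 | equals the maximum |
| Day -16 (SAP early edge) | 16 + 2 = 18 | well short of the maximum |
| Day -14 (planned day) | 14 + 2 = 16 | equals the minimum |
| Day -12 (protocol late edge) | 12 + 2 = 14 | below the minimum |

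The stated maximum of 32 days is reproduced only if Visit 1 may fall as early as Day -30. The duration thus confirms the protocol's early edge. It does not confirm the late edge, since the 16-day minimum matches Day -14; Day -12 rests on the +2 alone. The statements of about two weeks are too loose to settle either edge.

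**Step 2: compare the windows.**
- Protocol: -14 - 16 = -30 to -14 + 2 = -12, which is 30 - 12 + 1 = 19 calendar days.
- SAP: Days -16, -15 and -14, which is 3 calendar days, all inside the protocol window.
- Permitted by the protocol but outside the SAP range: Days -30 to -17 (14 days) and Days -13 and -12 (2 days), so 14 + 2 = 16 of 19.

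**Step 3: try the other reading of the SAP cell.** If -14 to -16 were offsets from the planned Day -14, the window would be Day -28 back to Day -30. That is again 3 of the 19 days, and it would exclude the planned day itself. If the entry is a slip for -16/+2, the cell simply needs correcting. Neither literal reading agrees with the protocol.

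**Step 4: trace the consequence.** A protocol-compliant date outside Days -16 to -14 reaches the SAP 12 summary only if it is judged against the SAP window. It affects the per-protocol population only if it is then also graded major. The primary analysis (SAP 16.1) uses all randomized subjects with observed data, and no readable rule includes or drops data by the date of Visit 1.

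**The case against.** The strongest reply is that this is a clerical slip in a descriptive table. SAP 12, 8 and 10.2 all speak of protocol deviations, and a date the protocol allows is not, in ordinary language, a deviation from the protocol. SAP 1 says that some design details are included only as background, so a table cell may not count as a directive that overrides the protocol. SAP 2 concerns analyses, and a restated visit window is not one. Any per-protocol effect requires the SAP window to be used and the breach to be graded major, and no readable text grades it so. Visit 1 precedes randomization, so an exclusion on this ground would not be driven by treatment. Sixteen of 19 counts days, not subjects, and both documents plan Day -14, which lies in both windows. The protocol schedule reproduced in SAP 4 cannot be read here and may carry the right window. Finally, since the duration does not support Day -12, one might ask the sponsor only to confirm and align the window.

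Most of this stands as a limit on the impact. It does not remove the conflict. Judging Visit 1 against the protocol's window would be sensible, but the SAP does not say so, and its precedence rule points the other way. The table is labelled as the acceptable window, and SAP 12 names the out-of-window category directly after saying that major deviations will be summarized. If the SAP 4 schedule does show the protocol's window, the SAP contradicts itself and 5.1 still needs correcting. On the late edge, the protocol states +2 in two places. Even if that edge is set aside, the 14 earlier days remain in conflict.

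**Conclusion.** The concern holds: the SAP 5.1 entry is wrong as written, with low impact. It covers 3 of the 19 days that the protocol permits for Visit 1, and no departure is declared.

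The effect on the intent-to-treat primary analysis is none. Protocol-compliant subjects could be misreported in the deviation summary if the SAP window is the one used. The per-protocol sensitivity analysis would change only if such deviations were also graded major; if graded minor, it is untouched. The share of subjects affected cannot be estimated, because neither document gives a distribution of Visit 1 dates.

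The conclusion rests on reading -16/+2 as days before and after Day -14. The 32-day maximum duration supports this for the early edge; the late edge depends on the protocol's stated +2.

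**What to change.** In the SAP 5.1 table, replace the Visit 1 window with Day -30 to Day -12 (Day -14, -16/+2), and assess out-of-window status for Visit 1 against that range. Do this before deviations are reviewed and treatment is unmasked, so that nobody has to choose between two windows during deviation grading. The cost is one table cell; trial conduct, data and the primary analysis do not change.
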